15.0 Data and Safety Monitoring Plan

15.2 * DATA AND SAFETY MONITORING PLAN: (REQUIRED)

All greater than minimal risk studies are required to provide a plan. Lack of an adequate plan is one of the most common reasons why IRB approval is delayed.

Instructions:

Describe the plan for monitoring data quality and participant safety. Key areas that should be included in the plan are:

- An explanation of the plan to monitor data collection, study progress, and safety
- A description of who will perform the monitoring and at what frequency (e.g., the PI only, a contract research organization, a Data and Safety Monitoring Board or Data Monitoring Committee, etc.)
- The type of data and events that will be reviewed (e.g., adverse events, breaches of confidentiality, unanticipated problems involving risk to participants or others, unblinded efficacy data, etc.)
- Procedures and timeline for communicating monitoring results to the UCSF IRB, the study sponsor, and other appropriate entities
- Assurance that the research team will adhere to the **UCSF IRB reporting requirements**

As appropriate:

- A plan for conducting and reporting interim analysis
- Clearly defined stopping rules
- Clearly defined rules for withdrawing participants from study interventions

The study participants will be followed bi-monthly for the first year and then as frequently as clinically indicated for the second year. Safety assessments will be done at every visit including vital signs, limited physical exam, safety check of the DBS device. Any Adverse Experience will be recorded and the subject diary will be reviewed to detect any adverse experiences. The Investigator will maintain constant vigilance over the study and review the data no less than on a monthly basis. The data will be presented and reviewed by the MSM at least every 6 months. Data will be presented and reviewed by the IRB annually.

Study stopping criteria are two or more patients with study related serious adverse events i.e. symptomatic intracranial hemorrhage, subdural hematoma, seizures, worsening neurological status, or death.

Subject stopping criteria would be (1) greater than 40% worsening on the Burke-Fahn-Marsden dystonia rating scale (BFMDRS) or the Barry Albright dystonia scale (BADS) that does not improve with programming changes (2) Depression that does not improve with programming changes or suicidality. Any patient that is withdrawn from the study will be followed as part of intention to treat analysis.

15.3 * DATA AND SAFETY MONITORING BOARD (DSMB): Will a Data and Safety Monitoring Board (DSMB) be established: (REQUIRED)

- Yes
 No

15.4 DSMB DETAILS: Provide details from the DSMB's charter, including meeting frequency, and affiliations and qualifications of members: If the DSMB has not yet been established, submit these details to us as they become available.

All AEs will also be reported to the, medical safety monitor (MSM) who is a neurosurgeon ([name]) within the institution with no direct involvement in this study but who have expertise in implantable devices. Treatment related adverse events assessed as definitely, probably, or possibly related to study procedures and either serious or unexpected, noted by any study personnel will be reported within 5 working days of their knowledge of the event to the MSM. The MSM will then advise the PI on potential changes in procedures to improve safety, or, in the event of multiple serious adverse events, may invoke stopping rules.

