A small cohort of 15 subjects will be implanted in the first two years. All participants will undergo a battery of clinical dystonia rating scales, measures of mobility, and quality of life measures performed prospectively pre- and post-DBS. Patients will also undergo a neuropsychological battery before surgery and 12 months post-operatively. The neuropsychological battery will be customized for each patient and his/her expressive language abilities. The subjects will be examined every two months for one year following surgery and adjustments to the stimulation parameters will be made. The DBS stimulation parameters will be patient-specific and calibrated by the dystonia, mobility and quality of life rating scales. The changes in dystonia and quality of life rating scales at the end of 1 year of treatment will be compared to historical results from published DBS of globus pallidus interna for secondary dystonia and used to design a future larger, randomized clinical trial. All dystonia scales measuring motor involvement will be videotaped so the tapes can later be reviewed if necessary.

7.5 BACKGROUND AND SIGNIFICANCE: Briefly provide the background and significance of this study (e.g. why is this study needed) (space limit: one half page):

If this is a first in humans study, please summarize the safety data from the animal studies. For pediatric drug or device studies, please identify if this is the first study in pediatric populations.

Dystonia is a movement disorder seen in both children and adults that is characterized by "sustained or intermittent muscle contractions causing abnormal, often repetitive, movements, postures, or both."¹ Secondary dystonia is far more common in pediatric populations than primary dystonia, and far more recalcitrant to standard pharmacologic and surgical treatments including Deep Brain Stimulation (DBS). There exists a large unmet need to develop new therapeutics, treatment strategies, and outcome measures for pediatric secondary dystonia².

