9.0 Sample Size and Eligibility Criteria

9.1 ENROLLMENT TARGET: How many people will you enroll:

17

If there are multiple participant groups, indicate how many people will be in each group:

9.3 SAMPLE SIZE JUSTIFICATION: Explain how and why the number of people was chosen. For multi-site studies, this is referring to the number that will be enrolled across all sites:

This is a phase I pilot study of 15 participants to determine safety and tolerability as well as estimate effect size to inform planning of future larger trials that will test effectiveness. There is not sufficient data on the efficacy outcome measures to calculate sample size using statistical methods, thus the number of subjects was estimated based on a similar prospective study of DBS of globus pallidus (GPI) in adults with secondary dystonia in which a significant improvement was found using 13 subjects. We will screen up to 17 patients to achieve a total of 15 implanted.

9.4 * PARTICIPANT AGE RANGE: Eligible age ranges: (REQUIRED)

- 0-6 years
- 7-12 years
- 13-17 years
- 18-64 years
- 65+

9.5 * STUDY POPULATIONS: Data will be collected from or about the following types of people (check all that apply): (REQUIRED)

- Inpatients
- Outpatients
- Family members or caregivers
- Providers
- People who have a condition but who are not being seen as patients
- Healthy volunteers
- Students

- Staff of UCSF or affiliated institutions
- None of the above

9.6 * SPECIAL SUBJECT GROUPS: Check the populations that may be enrolled: (REQUIRED)

- Children / Minors
- Subjects unable to consent for themselves
- Subjects unable to consent for themselves (emergency setting)
- Subjects with diminished capacity to consent
- Subjects unable to read, speak or understand English
- Pregnant women
- Fetuses
- Neonates
- Prisoners
- Economically or educationally disadvantaged persons
- None of the above

If not already addressed in the Background and Significance questions in the Research Plan section or elsewhere, explain why it is appropriate to include the types of subjects checked above in this particular study:

The intervention is aimed at children and young adults because data from Deep Brain Stimulation (DBS) in other sites in the brain (globus pallidus) suggests that the earlier in the disease course DBS is performed the better the outcome. DBS of globus pallidus has been shown to be safe and effective in children as young as 7 years of age.

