- Infection: We anticipate that the infection rate in this patient population may be higher than the infection rate in Parkinson's disease, Essential Tremor, and primary dystonia. This is due to known higher infection rates in children compared with adults and the presence of a mixed movement disorder with a greater amount of hyperkinetic movements as compared with other movement disorders patients.
- Patient growth necessitating lead/extension length revision
- Patient brain/skull growth leading to lead migration: In cases where growth of the brain and/or skull is not complete at time of implant, the distance from the lead anchor point (burr hole) to the target site increases with time and growth of the individual. As a result, lead migration relative to the target site may occur.
- Children should be advised to avoid games, sports and other pastimes where a strain to the lead /connector assembly or a percussive injury to system components may be likely to occur (e.g., soccer, football/rugby).
- Intracranial hemorrhage

- Hemiplegia/Hemiparesis
- Paresis/asthenia
- Worsening of Motor Impairment
- Trouble swallowing
- Sensory Impairment (e.g., pain, paresthesia, sensory disturbance, hypesthesia, hearing/tinnitus)
- Headache
- Speech/Language disturbances (e.g., dysarthria, hypophonia)
- Subcutaneous Hemorrhage/Seroma
- Cerebral Spinal Fluid Abnormality
- Eye visual disturbances (e.g., diplopia, abnormal vision, visual field defect) and eye disorders (e.g., twitching)
- Cognitive disturbances (e.g., thinking abnormal, confusion, alteration of mentation) and Neuropsychological disturbances (e.g., depression, anxiety)

14.2 RISKS: Describe any anticipated risks and discomforts not listed above:

Potential Risks

General risks of DBS surgery (risks incurred by any patient having DBS implantation surgery, within or outside of this protocol)

General Anesthesia

There are always risks with general anesthesia. This may include a reaction to medications, myocardial infarction, or even death. There may be unknown risks.

Risks of the surgical procedure

Implanting the neurostimulator system carries the same risks associated with any other brain surgery. Risks may include:

- Paralysis, coma, and/or death
- Bleeding inside the brain (stroke)
- Leaking of fluid surrounding the brain

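### One study-related death triggers no stop or hold on implants under the ordinary reading of 15.2 and 15.4, and the wording leaves room for a second threshold

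*Combined protocol and SAP*

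**What the plan says.** Section 15.2 gives the study stopping criteria in one sentence: "two or more patients with study related serious adverse events i.e. symptomatic intracranial hemorrhage, subdural hematoma, seizures, worsening neurological status, or death". The subject-level criteria that follow (more than 40% worsening on either dystonia scale, depression, suicidality) concern the individual patient and do not stop or pause the study.

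Section 15.4 describes what happens after an event. A treatment-related event that is serious or unexpected "will be reported within 5 working days of their knowledge of the event to the MSM". The response to that report is advice: "The MSM will then advise the PI on potential changes in procedures to improve safety". The same section gives the MSM a further power, which is discretionary and conditional: "in the event of multiple serious adverse events, may invoke stopping rules". Section 15.2 adds investigator review at least monthly, annual IRB review, and routine MSM review: "The data will be presented and reviewed by the MSM at least every 6 months".

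Death is a foreseen surgical risk in 14.2 ("Paralysis, coma, and/or death"), with no rate attached. On size, 7.4 states "A small cohort of 15 subjects will be implanted in the first two years", and 9.3 states "We will screen up to 17 patients to achieve a total of 15 implanted". Eligibility in 9.7 is 7 to 25 years.

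**The concern.** Safety and tolerability are the first aim (7.3), the target is new, and 7.6 reports no preliminary studies. The study-level stopping criterion is what should tell the investigator and the MSM when to stop implanting. As ordinarily read, it gives a death the same weight as a seizure: a second affected patient is needed before anything stops. Followed to the letter, the next implant could go ahead while the first death is still being reported and considered.

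The wording also leaves room for argument. If the closing words of the sentence are read as a criterion of their own, one death is enough. An investigator facing that event should not have to settle the threshold by interpreting a comma.

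**Working it through.** The documents state no event rate, error rate or operating characteristic for the criterion, so there is no figure of the plan's own to reproduce. The main check is textual. The arithmetic afterwards is illustration.

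**1. Apply the text to one study-related death.**

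| Provision | What it needs | One death in one patient |
|---|---|---|
| 15.2 study stopping, ordinary reading | at least 2 patients with a listed event | count is 1: not met |
| 15.2 study stopping, death read as a separate item | any death | met |
| 15.4 power to invoke stopping rules | multiple serious events; discretionary | one event: not met |
| 15.4 report and advice | one related serious or unexpected event | met: report within 5 working days, then advice to the PI |
| 15.2 subject stopping | scale worsening, depression, suicidality | concerns the individual, not the study |

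The connective before the list introduces the events being counted, and death is its last item. That makes the first row the more natural reading. No other section provides a stop, hold or pause after a single death.

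**2. Compare the units.** Section 15.2 counts patients and 15.4 counts events. A patient who has a symptomatic hemorrhage, then neurological worsening, then dies is one patient but arguably three events. That case fails 15.2 as ordinarily read, yet could satisfy 15.4. The two sections can therefore disagree about the same patient.

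**3. Illustration.** From the documents: n = 15 implanted. Assumed: d = per-patient risk of study-related death, and q = per-patient risk of any other listed event without death, independent between patients.

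- Chance of at least one death: 1 − (1 − d)^15.
- Chance that a death occurs and the two-patient criterion is never met (one patient dies, the other 14 have no listed event): 15 × d × (1 − d − q)^14.
- The second divided by the first is the chance, given a death, that the criterion is never met.

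At d = 1%, q = 5%: 1 − 0.99^15 = 0.140; 15 × 0.01 × 0.94^14 = 0.063; 0.063 / 0.140 = 0.45.

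| d | q | At least one death | Death and criterion never met | Never met, given a death |
|---|---|---|---|---|
| 0.5% | 0% | 0.072 | 0.070 | 0.97 |
| 1% | 5% | 0.140 | 0.063 | 0.45 |
| 2% | 10% | 0.261 | 0.050 | 0.19 |
| 2% | 20% | 0.261 | 0.009 | 0.04 |

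Seen from the time of a death, if the other 14 patients each have an assumed chance p of a listed event, the criterion is eventually met with probability 1 − (1 − p)^14: 0.25 at p = 2%, 0.51 at 5% and 0.77 at 10%.

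**The case against.** The strongest case on the other side is that a single death is far from ignored. A reader might infer that no review is required after it. The documents do not support that: 15.4 makes both the report and the MSM's advice mandatory after one related event, and the MSM is a neurosurgeon with no direct involvement in the study. What is missing is narrower, namely any hold on implants while that review takes place.

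A reader might also take the two-patient count for the plan's only quantitative safety boundary. It is the only study-level one; the 40% worsening rule is quantitative too, at subject level.

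The event wording of 15.4 could let the MSM act after one patient who had several serious events. That stands, but it is discretionary, it would not cover a sudden death without preceding events, and it shows that the two sections need reconciling.

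It is tempting to put a number on exposure by saying that a death at a random place among 15 leaves 7 more implants on average. That ignores the two-patient criterion itself, which an earlier or later event can trigger. At d = 1% and q = 5%, with events known before the next implant, the average is about 4 to 5. The documents support neither the rates nor that sequence, so no such figure is relied on here.

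The probabilities are also sensitive to q. The list includes seizures and the broad category of neurological worsening, so q could exceed 10%; at d = 2% and q = 20% the chance that the criterion is never met falls to about 4%.

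Finally, no standard cited in the documents demands a halt after one death, so the exact remedy is partly a design choice. The need for a single reading is not.

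**Conclusion.** The point holds as a gap and an ambiguity in the study-level stopping provisions. On the ordinary reading, one study-related death meets neither the two-patient count in 15.2 nor the multiple-event condition in 15.4. It leads to a report and advice, with no stop and no hold on further enrolment or implantation. A less natural reading makes one death enough, and the two sections count in different units.

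This conclusion rests on the text alone. Over the assumed ranges (d from 0.5% to 2%, q from 0% to 10%), the chance of at least one death in 15 is 7% to 26%, and the chance that the criterion is then never met is 19% to 97%. These ranges show only that the gap could matter; they do not estimate risk in this trial. The change should be made, at small cost.

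**What to change.** Reconcile 15.2 and 15.4 so that only one reading is possible:

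- In 15.2, take death out of the two-patient count and give it its own sentence: after a first study-related death, no new patient is enrolled or implanted until the MSM's review, which 15.4 already calls for, has been given in writing. Keep the two-patient count for the non-fatal events.
- In 15.4, state that the MSM's authority to invoke stopping rules covers a single study-related death as well as multiple events.
- Use the same unit, patients or events, in both sections.

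The cost is a sentence in each of the two sections and, if a death occurs, a possible short pause in enrolment. The change governs trial conduct only; care of patients already implanted is not affected.

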Please navigate back to section 4.0 Initial Screening Questions to change your answer to 4.4 about procedures involving radiation to 'Yes.' This will ensure that the Radiation Safety Committee receives a copy of your application when you first submit it to the IRB. Contact the [Radiation Safety Committee](#) if you are not sure if radiation is involved.

7.9 * PROCEDURES / METHODS: (REQUIRED)

For clinical research, list all study procedures, tests and treatments required for this study, including when and how often they will be performed. If there are no clinical procedures, describe the research activities.

If some of the activities would occur even if the person were not in the study, as in the case of treatment or tests performed for diagnostic purposes, clearly differentiate between those activities that will be done solely for research purposes and those that are happening as part of routine care.

Examples may include:

- additional scans outside standard clinical diagnosis or monitoring
- additional biopsies to collect tissue for research
- extra clinic visits
- extra lab tests not required for clinical care

If you have a procedure table, attach it to the submission with your other study documents.

Screening Visit (within 120 days of surgical date)

Clinical visit to determine initial eligibility for DBS therapy. This will include a clinical movement disorders neurology evaluation and/or a clinical surgical evaluation, including review of MRI brain.

Informed Consent

Written informed consent (and assent if indicated) will be obtained from all patients before enrollment in the study. All potential subjects and/or legal guardians will be properly informed as to the purpose of the study and the potential risks and benefits known or that can be reasonably predicted or expected and the option of undergoing DBS surgery outside of the study under an HDE. Key parts of the consent will be read out loud by a study investigator while the subject and/or guardian reads along and is asked if they understand the consent form. The Investigator will retain the original copy of the Informed Consent Form signed by the patient, and a duplicate will be provided to the patient.

Baseline Assessment

A baseline assessment will be completed prior to the DBS system implantation in all patients. Baseline evaluation will consist of reviewing/obtaining the following:

- Inclusion/Exclusion criteria
- Complete demographic information

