Neuropsychological testing: Baseline and one year follow up neuropsychological evaluation will be performed using standardized tests when possible. The testing will be customized to each child or young adult according his or her age and ability to communicate and access the materials physically. Attempts will be made to include the following test battery or comparable tests: (1) non-verbal intellectual abilities (Matrix Reasoning, Picture Concepts, and Picture Completion [subtests of the Wechsler Intelligence Scale for Children, the Wechsler Abbreviated Scale of Intelligence, and the Wechsler Pre-school and Primary Scale of Intelligence])(2) verbal intellectual abilities (Vocabulary, Similarities, Information, and Picture Vocabulary [subtests of the Wechsler Intelligence Scale for Children]) (3) memory (Memory for Faces, Dot Locations, and Digit Span [subtests of the Children’s Memory Scale]) and (4) mood/behavior (BASC-3: Self Report of Personality)

Attach any unpublished instruments in the 'Other Study Documents' section of the Initial Review Submission Packet form after completing the study application. Published instruments should NOT be attached.

7.12 * BIOSPECIMEN COLLECTION: Are you drawing any blood or collecting other biosamples (e.g. tissue, buccal swabs, urine, saliva, hair, etc.): (REQUIRED)

Yes No

7.25 STATISTICAL METHODS: Briefly summarize the methods and types of analyses that will be performed:

All of the dystonia clinical rating scale measures will be measured pre-operatively and post-operatively after 1 year of continuous stimulation and the measures at the two time points will be compared using the Wilcoxon signed-rank test for matched pairs.

7.26 REFERENCES: List only the 5-10 most relevant references (a separate bibliography can be attached for reference purposes if this study involves novel approaches, agents, or an emerging technology that the IRB may not be familiar with):

1. Mink JW. Special concerns in defining, studying, and treating dystonia in children. *Mov Disord.* 2013;28:921-925. doi:10.1002/mds.25548.
2. Sironi VA. Origin and evolution of deep brain stimulation. *Front Integr Neurosci.* 2011;5:42. doi:10.3389/fnint.2011.00042.

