Describe the additional safeguards that have been included in the study to protect the rights and welfare of these subjects and minimize coercion or undue influence:

Here are some examples:

- evaluating capacity to consent for individuals who may be decisionally impaired (specify how)
- calibrating payment amounts to be non-coercive for the financially disadvantaged
- conducting more in-depth evaluations of subjects' understanding of the study and the voluntary nature of participation
- involving advocates in the consent process

More information and other safeguards are described here: **Vulnerable Subject Populations** and **Recruiting Staff and Students**.

Children and adolescents ages 7-17 will be asked to give verbal assent to the procedure. Subjects age 18 and over who are unable to give informed consent will have a surrogate give informed consent on their behalf.

9.7 INCLUSION CRITERIA: Briefly describe the population(s) that will be involved in this study. Include anyone that data will be collected from or about (e.g. patients, healthy controls, caregivers, providers, administrators, students, parents, family members, etc.):

1. Male or female between 7-25 years of age at Visit 2 (day of surgery).
2. Documentation of a secondary dystonia diagnosis as determined by a fellowship trained movement disorders specialist, including either abnormality on brain MRI or history of hypoxic-ischemic brain injury preceding onset of dystonia symptoms.
3. Symptoms present for at least 6 months.

4. Written informed consent and assent (when applicable) obtained from participant or participant's legal representative and ability for participant to comply with the requirements of the study.
5. Dystonia symptoms that are sufficiently severe, in spite of best medical therapy, to warrant surgical implantation of deep brain stimulators in the clinical opinion of the treating physician
6. Minimum score of Burke-Fahn-Marsden Rating Scale and/or Barry-Albright Dystonia Rating Scale of 6.
7. Stable doses of anti-dystonia medications (such as levodopa, baclofen, or diazepam) for at least 30 days prior to baseline assessment
8. If participant receives botulinum toxin injections, patient should be on a stable injection regimen (as defined as no changes in past 4 months)
9. Intact thalamic anatomy as determined by standard clinical MRI in the past 2 years.
10. Patient has been clinically determined to be a good candidate for deep brain stimulation.

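### The more-than-40% worsening rule for withdrawing a subject, read against pre-operative baseline, cannot be met by a patient whose baseline is at or above about 71.4% of the maximum on both scales

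*Combined protocol and SAP*

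**What the plan says.** Section 15.2 gives two subject stopping criteria. The first is "greater than 40% worsening on the Burke-Fahn-Marsden dystonia rating scale (BFMDRS) or the Barry Albright dystonia scale (BADS") where programming changes bring no improvement. The second concerns depression and suicidality. The first does not say which earlier score the worsening is measured from, and it has no absolute-change or clinical-judgement alternative.

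Other places that bear on the rule:

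- Section 7.9, Baseline Assessment: "A baseline assessment will be completed prior to the DBS system implantation in all patients". No other assessment is named as the baseline.
- Section 7.25, the only planned comparison of scores: "All of the dystonia clinical rating scale measures will be measured pre-operatively and post-operatively after 1 year of continuous stimulation".
- Section 9.7, criterion 6: "Minimum score of Burke-Fahn-Marsden Rating Scale and/or Barry-Albright Dystonia Rating Scale of 6". No upper limit is set.
- Section 9.7, criterion 5: "Dystonia symptoms that are sufficiently severe, in spite of best medical therapy, to warrant surgical implantation of deep brain stimulators".
- Section 15.2, at study level: "Study stopping criteria are two or more patients with study related serious adverse events".
- Section 15.4: "All AEs will also be reported to the, medical safety monitor (MSM"), who advises the principal investigator and, "in the event of multiple serious adverse events, may invoke stopping rules".

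**The concern.** A relative threshold on a bounded scale has a ceiling. The higher a patient starts, the less room is left, and beyond some baseline the required percentage rise no longer fits on the scale. The trial enrols patients whose dystonia is bad enough for brain surgery and sets no upper score limit, so high baselines are allowed.

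The rule therefore works backwards. A patient at the entry floor meets the threshold after a small rise in points, while the most severe patients may be unable to meet it however much they deteriorate. Section 14.1 lists worsening motor impairment among the risks, so this is an anticipated harm. At stake is whether every subject has a working withdrawal trigger for it.

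**Working it through.** The plan attaches no calculation to this rule, so there is no figure of its own to reproduce.

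**Inputs from the documents**

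- Threshold: more than 40%, on either scale (15.2).
- Entry floor: 6, with no maximum (9.7).
- Planned number implanted: 15 (9.3).

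**Assumptions**

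- Each scale starts at 0, is bounded, and scores higher as worse. The documents give no scale ranges, but using a minimum score as a severity floor fits higher being worse.
- The 40% is a relative change from the pre-operative baseline. Sections 7.9 and 7.25 make this the natural reference.

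**Where the rule stops working.** Let f be the baseline as a fraction of the scale maximum. The rule needs a later score above 1.4 × f, and no score can exceed 1. So it can be met only if 1.4 × f < 1, that is f < 1/1.4 = 0.7143. No scale maximum is needed, because the bound is a fraction of whatever that maximum is.

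The largest possible worsening is (1 − f)/f.

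| Baseline, share of maximum | Score needed (1.4 × f) | Largest possible worsening |
|---|---|---|
| 60% | above 84% | 66.7% |
| 65% | above 91% | 53.8% |
| 70% | above 98% | 42.9% |
| 71% | above 99.4% | 40.8% |
| 75% | above 105%, impossible | 33.3% |
| 80% | above 112%, impossible | 25.0% |
| 90% | above 126%, impossible | 11.1% |

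**Rounding.** The exact bound is 71.43%. At exactly 71.4% the trigger is 1.4 × 0.714 = 99.96%, which the maximum score alone would meet. For a whole-point scale with a maximum below 500, no attainable score falls between 71.4% and the exact bound.

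**Contrast at the entry floor.** 6 × 1.4 = 8.4, so a rise of more than 2.4 points meets the threshold.

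**Either-scale wording.** A patient above the bound on one scale can still trigger on the other. The rule is wholly out of reach only when both baselines are at or above the bound.

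**Sensitivity to the reading.** Two illustrations, neither supported by the text:

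- If 40% meant 40% of the scale maximum, the unreachable point would fall to 1 − 0.40 = 60% of maximum.
- If worsening were measured from a later score improved by 23% (the average improvement cited in 4.1), the pre-operative unreachable point would rise to 0.7143/(1 − 0.23) = 92.8%.

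A ceiling remains in both.

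**The case against.** The strongest reply is that the real defect is the missing reference score, and that the ceiling follows from one reading of it. Section 7.9 also has both scales rated at the first post-operative visit before the device is switched on. Because the rule is tied to reprogramming, that score is a credible reference. This is fair as far as it goes. But the plan never calls that rating a baseline, and using it would apply the same 71.4% ceiling to a different score.

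Second, no affected patient is shown. Being severe enough for surgery does not mean scoring above 71.4% of maximum on two scales. This stands, and it limits the severity of the point.

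Third, other protection exists. Worsening neurological status is among the events that count towards the study-level rule. Related adverse events that are serious or unexpected reach the medical safety monitor within 5 working days, and the monitor then advises on that single case. Both scales are scored about every 8 weeks, the investigator reviews data at least monthly, and stimulation can be reduced or turned off. All of this is true and reduces the consequence, but none of it is a withdrawal rule for one worsening patient.

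Last, a judgement limb open to every subject makes an objective rule partly discretionary in an open-label study, and an alternative limited to high baselines would be narrower. The cost is real. However, a limb limited to baselines above the bound would leave out the patient at 70%, who needs a score above 98%. The 40% limb stays as an objective trigger.

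**Conclusion.** The concern holds and is minor. A patient at or above about 71.4% of the maximum on both scales has no subject-level trigger for withdrawal because of motor worsening, and a patient just below has one in name only. Nothing in the eligibility criteria keeps such a patient out.

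The conclusion rests on the pre-operative reference and on zero-based, bounded scales where higher is worse. Confidence is medium because the plan states neither. The documents give no baseline distribution, so the number of patients affected cannot be estimated. The gap lies in a stated safety rule and does not touch the efficacy analysis.

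**What to change.** In 15.2, replace criterion (1) with:

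> (1) a BFMDRS or BADS score more than 40% above the subject's pre-operative baseline score on the same scale, or, whatever the percentage change, motor worsening from pre-operative baseline recorded as an adverse event that the investigator, after consulting the medical safety monitor, judges clinically significant; in either case, worsening that does not improve with programming changes.

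This names the reference score and keeps the 40% threshold. The second limb does not depend on the baseline level, so it leaves no cliff just below 71.4%. The decision stays with the investigator. The monitor is only consulted, a step that 14.3 already uses for unresolved cognitive change.

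The cost is one sentence. Section 9.7 is unchanged, no assessment or visit is added, and the monitor already receives all adverse events under 15.4. The downside is some clinical judgement in the withdrawal rule, plus one consultation whenever the second limb is used.
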